6.20. Criteria for Discontinuation of Study Drug

Study drug must be discontinued in the following instances:

- Liver-related clinical event that warrants discontinuation as determined by the Hepatic Events Adjudication Committee.
- Subject develops an SAE consisting of a serious hypersensitivity reaction to study drug.
- Subject experiences diarrhea that meets the criteria in [Section 6.24](#) for discontinuation.
- Subject experiences a Grade IV Common Terminology Criteria for Adverse Events (CTCAE) or meets the criteria for Drug Induced Liver Injury described in [Section 6.26](#).
 - The Data Monitoring Committee (DMC) should perform a causality assessment. The study drug may be restarted if the DMC concludes that the AE or laboratory abnormalities were not related to study drug, the AE has resolved, laboratory abnormalities have returned to baseline, and the subject is amenable to close clinical follow-up.
 - If, after re-challenge, a subject has a second AE or recurrent elevations (even mild or minimal) of total bilirubin, ALT, or AST as defined in [Section 6.26.3](#), study drug should be discontinued permanently.

- Unacceptable toxicity or toxicity that, in the judgment of the Investigator or the Sponsor, compromises the ability to continue study-specific procedures or is considered to not be in the subject's best interest.
- Significant subject noncompliance including refusal to complete the Week 24 liver biopsy.
- Significant protocol violation that impacts subject safety.
- Pregnancy during the study; refer to [Appendix D](#).
- Discontinuation of the study at the request of Akero, a regulatory agency, or an IRB/IEC/EC.

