6.22. Adverse Events

An AE is any unfavorable and unintended sign (including an abnormal laboratory finding), symptom, or disease temporally associated with the use of a study drug, whether or not related to the study drug. AEs may also include pre- or post-treatment complications that occur as a result of protocol specified procedures, lack of efficacy, overdose, drug abuse/misuse reports, or occupational exposure. Pre-existing events that increase in severity or change in nature during or as a consequence of participation in the clinical study will also be considered AEs. AEs that occur after the first dose of EFX or during the study treatment and safety follow up periods will be documented on the AE eCRF. The Investigator will assess the AE severity and relationship of the AE to study drug. The Investigator will treat the subject as medically required.

Laboratory values that are outside the laboratory reference range of normal should be reported as AEs only if considered clinically significant by the Investigator.

From the time of obtaining informed consent until 30 days after the last administration of study drug, all SAEs and non-serious AEs related to protocol-mandated procedures will be recorded on the SAE/AE eCRF. All other untoward medical occurrences observed during screening, including exacerbation or changes in medical history, will be captured on the medical history eCRF. Details on recording and reporting AEs are provided below.

Clinical judgment of the Investigator should be used to determine whether a subject is to be withdrawn due to an AE. In the event the subject requests to withdraw from study-related

treatment or the study due to an AE, the subject should be followed for the safety follow up period as outlined in the Schedule of Assessments.

All subjects experiencing AEs, including clinically significant abnormal laboratory values, whether or not associated with use of the study drug, must be monitored until the condition returns to normal, returns to the subject's baseline, until the Investigator determines the AE has reached a stable outcome and is no longer clinically significant, or the subject is considered lost to follow up.

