6.22.1. Severity

All AEs, both serious and non-serious, will be assessed for severity using the Common Terminology Criteria for Adverse Events (CTCAE) Version 5.0. The CTCAE scale includes unique clinical descriptions of AEs that are categorized by anatomy and/or pathophysiology and is provided in the Site Operations Manual.

The CTCAE scale displays Grades 1 through 5 with unique clinical descriptions of severity for each AE (including abnormal laboratory values) based on this general guideline provided in the CTCAE scale. For any AEs not covered by CTCAE the conventional definition of severity will be used.

- Grade 1 (Mild) AE: minor; no specific medical intervention; marginal clinical relevance
- Grade 2 (Moderate) AE: minimal intervention; local intervention; non-invasive intervention
- Grade 3 (Severe) AE: significant symptoms requiring hospitalization or invasive intervention
- Grade 4 (Life-threatening or disabling) AE: Complicated by acute, life-threatening complications; need for intensive care or emergent invasive procedure
- Grade 5 AE: Fatal

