6.22.5. Serious Adverse Events

6.22.5.1. Definition

A SAE is defined by federal regulation as any AE occurring at any dose that results in any of the following outcomes: death, life-threatening AE, in-patient hospitalization or prolongation of existing hospitalization, a persistent or significant incapacity or substantial disruption of the ability to conduct normal life functions, or a congenital anomaly/birth defect.

Important medical events that may not result in death, be life threatening, or require hospitalization may be considered an SAE when, based upon appropriate medical judgment, they may jeopardize the subject, and may require medical or surgical intervention to prevent one of the outcomes listed in this definition. Examples of such medical events include

allergic bronchospasm requiring intensive treatment in an emergency room or at home, blood dyscrasias or convulsions that do not result in inpatient hospitalization, or the development of drug dependency or drug abuse.

A life-threatening AE is one that, in the view of the Investigator, places the subject at immediate risk of death from the reaction as it occurred.

An unexpected AE is any event for which the specificity or severity is not consistent with the AE profile in the current EFX IB.

All SAEs, regardless of cause(s) or relationship to study drug, must be reported immediately to the study Sponsor and/or designee.

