- For Grade 3 clinically significant laboratory abnormality or clinical event, investigational medicinal product may be continued if the event is considered to be unrelated to investigational medicinal product.

- For a Grade 3 clinical event, or clinically significant laboratory abnormality confirmed by repeat testing, that is considered to be related to investigational medicinal product, investigational medicinal product should be withheld until the toxicity returns to \leq Grade 2.
- If a laboratory abnormality recurs to \geq Grade 3 following re-challenge with investigational medicinal product and is considered related to investigational medicinal product, then investigational medicinal product should be permanently discontinued, and the subject managed according to local practice. Recurrence of laboratory abnormalities considered unrelated to investigational medicinal product may not require permanent discontinuation.

Grade 4 Laboratory Abnormality or Clinical Event

- For a Grade 4 clinical event or clinically significant Grade 4 laboratory abnormality confirmed by repeat testing, the DMC should perform a causality assessment. The investigational medicinal product may be restarted if the DMC concludes that the AE or laboratory abnormalities were not related to study drug, the AE has resolved, laboratory abnormalities have returned to baseline, and the subject is amenable to close clinical follow-up.
- If a laboratory abnormality recurs to \geq Grade 4 following re-challenge with investigational medicinal product and is considered related to investigational medicinal product, then investigational medicinal product should be permanently discontinued, and the subject managed according to local practice. Recurrence of laboratory abnormalities considered unrelated to investigational medicinal product may not require permanent discontinuation.
- If, after re-challenge, a subject has a second serious AE or recurrent elevations (even mild or minimal) of total bilirubin, ALT, or AST as defined in [Section 6.20](#), investigational medicinal product should be discontinued permanently.

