6.26.3. Close Observation for Suspected Drug-Induced Liver Injury

For all subjects, close observation for suspected drug-induced liver injury includes the following within 72 hours of suspected drug-induced liver injury:

- Repeating liver enzyme (ALT, AST, and alkaline phosphatase) and serum bilirubin tests 2 or 3 times weekly.
- The frequency of repeat testing can decrease to once a week or less if abnormalities stabilize or the study drug has been discontinued and the subject is asymptomatic.
- Obtaining a more detailed history of symptoms and prior or concurrent diseases.
- Obtaining a history of concomitant drug use (including nonprescription medications and herbal and dietary supplement preparations), alcohol use, recreational drug use, and special diets.
- Ruling out acute viral hepatitis types A, B, C, D, and E; autoimmune or alcoholic hepatitis; hypoxic/ischemic hepatopathy; and biliary tract disease.
- Obtaining a history of exposure to environmental chemical agents.
- Obtaining additional tests to evaluate liver function, as appropriate (e.g., INR, direct bilirubin).
- Considering gastroenterology or hepatology consultations.
- Subjects who live far from study sites can be evaluated locally for history, physical exam, and laboratories, provided results can be communicated promptly to the site Investigator.

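### After a DMC-permitted restart, Protocol 6.20 and 6.24 set different triggers for permanent discontinuation, and the liver-elevation definition that both cite is not at the place cited

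*Protocol*

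**What the plan says.** Protocol 6.20 lists when study drug must be discontinued. One bullet covers a Grade 4 event or the DILI criteria of 6.26. Its sub-bullets ask the DMC for a causality assessment and allow a restart if the event is judged unrelated, has resolved, and the other conditions are met. The next sub-bullet gives the condition for a permanent stop: "If, after re-challenge, a subject has a second AE or recurrent elevations (even mild or minimal) of total bilirubin, ALT, or AST". It says that these elevations are defined in 6.26.3.

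The Grade 4 block of 6.24 (Toxicity Management) starts from the same point: "For a Grade 4 clinical event or clinically significant Grade 4 laboratory abnormality confirmed by repeat testing, the DMC should perform a causality assessment". The restart conditions match those of 6.20. The condition for a permanent stop is then: "If, after re-challenge, a subject has a second serious AE or recurrent elevations (even mild or minimal) of total bilirubin, ALT, or AST". Here the elevations are said to be defined in 6.20.

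A separate bullet in the same 6.24 block covers laboratory abnormalities that recur to Grade 4 or above after re-challenge. If considered related, drug is stopped permanently. If unrelated, a permanent stop may not be needed.

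Section 6.26.3, where the reference ends, introduces its list as follows: "close observation for suspected drug-induced liver injury includes the following within 72 hours of suspected drug-induced liver injury".

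**The concern.** The two sections govern the same sequence of Grade 4 event, DMC assessment and restart, yet one turns on an AE and the other on a serious AE. This is an operative safety rule. Across about 55 planned sites (3.2), the section a site follows could decide whether a re-challenged subject stays on drug. The liver limb of both sentences depends on a definition that a reader cannot find at the place cited. The SAP does not address re-challenge, so it does not settle the question.

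**Working it through.** No arithmetic applies. The check compares the texts and follows each cross-reference to its end.

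**Step 1: definitions.** Section 6.22: "An AE is any unfavorable and unintended sign (including an abnormal laboratory finding), symptom, or disease temporally associated". Seriousness is judged by outcome (6.22.5.1), including "death, life-threatening AE, in-patient hospitalization or prolongation of existing hospitalization". Severity is graded separately (6.22.1), for example "Grade 3 (Severe) AE: significant symptoms requiring hospitalization or invasive intervention". Grade and seriousness are therefore different scales.

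**Step 2: two readings of 6.20.** Literal: a second AE is any AE as defined in 6.22. Narrow: because the sentence is nested under the Grade 4/DILI bullet, it means a second Grade 4 or DILI event.

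**Step 3: apply each rule to an event after restart.**

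| Event after restart | 6.20 literal | 6.20 narrow | 6.24 Grade 4 block |
|---|---|---|---|
| Non-serious AE below Grade 4, not liver-related | stop | not triggered | not triggered |
| Grade 3 AE with in-patient hospitalization | stop | not triggered | stop (serious) |
| Serious Grade 4 AE | stop | stop | stop |
| Non-serious Grade 4 laboratory recurrence, related | stop | stop | stop (separate bullet) |
| Non-serious Grade 4 laboratory recurrence, unrelated, other than bilirubin, ALT or AST | stop | stop | may not need a permanent stop |
| New non-serious Grade 4 laboratory abnormality, other than bilirubin, ALT or AST | stop | stop | not clearly triggered |

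The laboratory rows assume an abnormality that is clinically significant and confirmed by repeat testing, so that it counts as an AE.

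On the literal reading, the AE limbs of the two sentences differ for every non-serious AE. Only the related Grade 4 laboratory recurrence reaches the same result by another route. On the narrow reading, row 1 agrees, but rows 2, 5 and 6 do not. Row 2 diverges in one direction (6.24 stops, 6.20 does not) and rows 5 and 6 in the other. Neither re-challenge sentence carries a relatedness condition, so 6.20 does not make the exception for unrelated laboratory recurrences that 6.24 makes.

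**Step 4: the liver-elevation reference.** The chain has two links: 6.24 to 6.20, then 6.20 to 6.26.3. Section 6.26.3 has 9 bullets (repeat testing, history, exclusion of other causes, consultation and similar steps). Definitions of a bilirubin, ALT or AST elevation among them: 0.

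**Step 5: where thresholds do exist.** Section 6.26.1 (normal baseline) uses ALT above 5 or 8 times ULN and total bilirubin above 2 times ULN. Section 6.26.2 (abnormal baseline) uses ALT above 3 or 5 times baseline, or at least 300 or 400 U/L, with total bilirubin above 2 times ULN. Neither sets an AST threshold, although both re-challenge sentences name AST. It is also unclear how thresholds of this size fit with a sentence that counts even mild or minimal elevations. The reference point matters, because inclusion criterion 3 (Protocol 4.2) admits ALT and AST up to 5 times ULN.

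**The case against.** Several counter-arguments have force.

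- *The narrow reading is the natural one.* The preceding sub-bullet of 6.20 uses the term AE for the qualifying event, and 6.24 lets drug continue for Grade 1 and 2 events at the Investigator's discretion. A reader might infer that 6.20 forces a permanent stop for any trivial AE. The wording allows that, but the context speaks against it, so the point does not rest on it. Most Grade 4 clinical events would also be serious.
- *Both rules can be obeyed.* Neither sentence says *only if*, so stopping when either is met breaches neither. A reader might infer opposing instructions, and the re-challenge sentences do not go that far. A site that follows only one section would still treat the same event differently.
- *Grade 4 laboratory recurrences.* A reader might infer that 6.24 leaves all non-serious ones uncovered. It does not: related recurrences are stopped by the separate bullet, and bilirubin, ALT and AST fall under the limb shared by both sections. Only rows 5 and 6 remain.
- *Liver thresholds.* A reader might infer that the protocol has none. It has them for ALT and total bilirubin, within the 6.26 that the parent bullet cites. A site could also act on any recurrence without a cut-off. But then the reference to a definition has no function, and AST remains without a threshold.
- *Diarrhea.* Section 6.20 also contains "Subject experiences diarrhea that meets the criteria in" followed by a reference to 6.24, which never names diarrhea. A reader might infer missing criteria. The grade-based rules for clinical events in 6.24 largely answer this, so it is not part of the point.
- *Safeguards.* A restart needs a DMC finding that the event was unrelated, toxicity questions go to the Medical Monitor, and the Investigator may remove a subject from treatment at any time. This limits the consequences, but all three work from the same unreconciled text.

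**Conclusion.** The inconsistency is real and should be fixed. There is one trigger mismatch, present on both readings of 6.20. On the narrow reading it comes down to a Grade 3 event with in-patient hospitalization, and to a non-serious Grade 4 laboratory abnormality (other than bilirubin, ALT or AST) that is unrelated or new. There is one two-link reference chain that ends without a definition. These results rest only on the current, unredacted protocol text.

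The affected group is probably small: subjects restarted after a Grade 4 event whose second event falls in the gap. The documents give no re-challenge frequency, so no rate is claimed. A reader might look for a consequence for the primary endpoint or a planned test. Nothing here supports one, and none is claimed.

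**What to change.** Reconcile Protocol 6.20, the Grade 4 block of 6.24, and 6.26.1 to 6.26.3:

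1. State one re-challenge rule in one place and cross-reference it from the other. It should say whether the second event is judged by grade, by seriousness or as any AE, and whether relatedness matters.
2. Point the liver-elevation reference to a section that contains the definition and covers every analyte named, or remove the words that promise a definition.

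The clinical team decides the content; no clinical rule is proposed here. The cost is protocol wording or a site clarification, with no added procedures, visits or subjects. If dosing has already ended, what remains is to record which section was applied to any re-challenged subject.

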6.21. Interruption of Study Drug

If dosing is interrupted (i.e., as a result of an AE or intercurrent illness that would affect assessments of clinical status to a significant degree), every attempt should be made to keep the subject in the study and continue to perform the required study-related procedures. Discussion with the Medical Monitor is recommended. If this is not possible or acceptable to the subject or Investigator, the subject may be withdrawn from the study.

6.22. Adverse Events

An AE is any unfavorable and unintended sign (including an abnormal laboratory finding), symptom, or disease temporally associated with the use of a study drug, whether or not related to the study drug. AEs may also include pre- or post-treatment complications that occur as a result of protocol specified procedures, lack of efficacy, overdose, drug abuse/misuse reports, or occupational exposure. Pre-existing events that increase in severity or change in nature during or as a consequence of participation in the clinical study will also be considered AEs. AEs that occur after the first dose of EFX or during the study treatment and safety follow up periods will be documented on the AE eCRF. The Investigator will assess the AE severity and relationship of the AE to study drug. The Investigator will treat the subject as medically required.

Laboratory values that are outside the laboratory reference range of normal should be reported as AEs only if considered clinically significant by the Investigator.

From the time of obtaining informed consent until 30 days after the last administration of study drug, all SAEs and non-serious AEs related to protocol-mandated procedures will be recorded on the SAE/AE eCRF. All other untoward medical occurrences observed during screening, including exacerbation or changes in medical history, will be captured on the medical history eCRF. Details on recording and reporting AEs are provided below.

Clinical judgment of the Investigator should be used to determine whether a subject is to be withdrawn due to an AE. In the event the subject requests to withdraw from study-related

treatment or the study due to an AE, the subject should be followed for the safety follow up period as outlined in the Schedule of Assessments.

All subjects experiencing AEs, including clinically significant abnormal laboratory values, whether or not associated with use of the study drug, must be monitored until the condition returns to normal, returns to the subject's baseline, until the Investigator determines the AE has reached a stable outcome and is no longer clinically significant, or the subject is considered lost to follow up.

6.22.1. Severity

All AEs, both serious and non-serious, will be assessed for severity using the Common Terminology Criteria for Adverse Events (CTCAE) Version 5.0. The CTCAE scale includes unique clinical descriptions of AEs that are categorized by anatomy and/or pathophysiology and is provided in the Site Operations Manual.

The CTCAE scale displays Grades 1 through 5 with unique clinical descriptions of severity for each AE (including abnormal laboratory values) based on this general guideline provided in the CTCAE scale. For any AEs not covered by CTCAE the conventional definition of severity will be used.

- Grade 1 (Mild) AE: minor; no specific medical intervention; marginal clinical relevance
- Grade 2 (Moderate) AE: minimal intervention; local intervention; non-invasive intervention
- Grade 3 (Severe) AE: significant symptoms requiring hospitalization or invasive intervention
- Grade 4 (Life-threatening or disabling) AE: Complicated by acute, life-threatening complications; need for intensive care or emergent invasive procedure
- Grade 5 AE: Fatal

6.22.2. Relationship

The Investigator or qualified sub-Investigator is responsible for assessing the relationship to study drug using clinical judgment and the following considerations:

- Not related: all AEs should be considered related unless the AE is clearly unrelated to study drug or clearly due to the subject's underlying disease. For a SAE, an alternative causality must be provided (e.g., preexisting condition, underlying disease, intercurrent illness, or concomitant medication).
- Related: There is reasonable possibility that the event may have been caused by the study drug.

Ineffective treatment should not be reported as an AE.

The relationship to study-related procedures (e.g., invasive procedures such as venipuncture or biopsy) should be assessed using the following considerations:

- Not related: Evidence exists that the AE has an etiology other than the study procedure.
- Related: The AE occurred as a result of study procedures.

6.22.3. Study Stopping Rules

The DMC will be convened based on emerging safety data if any of the following occur:

- One or more subjects develop the same treatment-emergent grade 5 adverse event or lab abnormality (confirmed by repeat testing) deemed related to EFX.
- Two or more subjects develop the same treatment-emergent grade 4 or higher adverse event or lab abnormality (confirmed by repeat testing) deemed related to the same dose level of EFX.
- Three or more subjects develop the same treatment-emergent grade 3 or higher adverse event or lab abnormality (confirmed by repeat testing) deemed related to the same dose level of EFX.

The DMC will assess the causality and clinical relevance of the adverse events or lab abnormalities and recommend to either halt study dosing for all subjects, pause randomization, or take no action. If randomization or dosing is paused, it may be resumed (with or without modifications) only after further review of all available safety data and agreement by the appropriate regulatory agencies.

